### **9.2.1. Data Management**

A screening log will be utilized to track potential participants and record the counts of individuals approached, consented, meeting inclusion/exclusion criteria, withdrawals, and completion. A copy of the PICF will be stored in a secure room in a locked filing cabinet separate from the CRFs. Any potentially identifying information obtained in connection with this clinical trial will remain confidential and will only be used for the purpose of this clinical trial and it will only be disclosed with your permission, except as required by law. The information collected is classified as re-identifiable with identifying details replaced with a code). There investigators can link the code back to you if necessary, under extenuating circumstances (e.g. safety concerns). The code will be stored separately from the data. The information collected in this clinical trial will be entered into a database, using the code rather than your personal identifiable details. The clinical trial team, regulatory authorities, and Metro South Human Research Ethics Committee (HREC) and site Governance, The clinical trial team, regulatory authorities, and Metro South Human Research Ethics Committee (HREC) and site Governance will be able to inspect and have access to confidential data that identifies you by name. Any analysis, interpretation and publication of the study results will not identify individuals.

The paper files from interviews and from sessions will be stored in locked filing cabinets in a dedicated research office. Computer files will be kept on a password-protected computer at a designated site (which has high level security). Only approved clinical trial staff, Metro South Human Research Ethics Committee and site Governance may access your data. Records relating to the results of the trial will be kept for 7 years. After the 7-year period your paper records will be shredded and destroyed, and computer files deleted from the CRFs.

### **9.2.2. Monitoring and Quality Assurance**

The investigator will submit to the Reviewing HREC, annual (or more frequent if requested) reports of the study. Senior staff of the Queensland Centre for Mental Health Research will undertake regular quality checks to ensure consent.

## **10. Investigator Responsibility**

The Coordinating Principal Investigator will be responsible for the conduct of all aspects of the study. The study and its associated documents will be reviewed and approved by the appointed certified HREC and Research Governance (at all sites) before study start.

Prior to submission to appointed HREC and Research Governance, the investigator will sign the protocol signature page confirming her agreement to conduct the study in accordance with the protocol, GCP and other regulatory requirements locally applicable. All relevant data and records will be provided to the HREC as required.

## **11. Study Report**

The Investigator will submit at least annual study reports to the reviewing HREC, or more frequent if required.

## **12. Administrative Procedures**

### **Ethical Considerations**

All documentation pertaining to the study must be prepared in accordance with the requirements outlined by the relevant ethics committee. All documentation must then be approved or given a favourable opinion in writing by an HREC as appropriate.

The study will be performed in accordance with ethical principles that have their origin in the Declaration of Helsinki and are consistent with ICH/Good Clinical Practice, applicable regulatory requirements. The NHMRC National Statement on Human Research will also be utilised.

The Cognitive Remediation interventions are designed to be enjoyable and engaging with an emphasis on strategy rather than performance scores. The programs recognise that people with

schizophrenia spectrum disorders have often had repeated experiences of failure in learning situations and therefore the training of therapists and program designs emphasise doing your personal best and normalising cognitive strengths and weaknesses

### **Ethical Review Committee**

The National Ethics Application Form (NEAF) and associated documents will be submitted for approval to the appointed multi-site HREC and written approval obtained from both the appointed HREC and Governance Office, before volunteers are recruited and participants are enrolled. The Coordinating Principal Investigator will submit the National Ethics Application Form and associated documents including Site Specific Applications from each site, to the appointed HREC and Research Governance. The Coordinating Principal Investigator has overall responsibility to ensure all reports at each site are submitted in line with the appointed HREC reporting requirements.

### **Informed Consent**

Our criteria will ensure that recruited participants will be sufficiently competent to consent and participate in the study or to refuse consent. Current research provides evidence that while psychotic symptoms may be present, these do not robustly predict an individual's functionality in daily life and capacity to make decisions, and whilst strongly correlated with cognitive impairment, do not reflect an enduring inability to understand information related to research participation.

### **Participant Reimbursement**

There are no additional costs associated with participating in this research project, nor will participants be paid.

Participants may be reimbursed for any reasonable travel, parking, meals and other expenses associated with the research project visit.

### **Notification of Primary Care Physician**

It is desirable that the participants local doctor and/ or treating team be advised of their decision to participate in this research project.

### **Intellectual Property (IP) and Licencing**

The collection of data in this study is subject to Intellectual Property (IP) and Licencing agreements which will be documented in the Research Agreement. Publication Policy

De-identified results will be disseminated in peer reviewed publications, published in international journals and conferences.

### **Protocol Amendments**

Any amendments to the protocol will be submitted to the appointed HREC by the Coordinating Principal Investigator for approval. Any approved amendments by the appointed HREC will be

forwarded by the Coordinating Principal Investigator for submission to each Research Governance Office.

No changes (amendments) to the Protocol will be implemented without prior approval from the Reviewing Ethics Committee. If a Protocol amendment requires changes to the Informed Consent Form, the revised Informed Consent Form, prepared by the Coordinating Principal Investigator, will be approved by the Reviewing Ethics Committee and site governance officers.

Once the final Protocol has been issued and signed by the Coordinating Principal Investigator and the authorised signatories, it will not be informally altered. All protocol amendments will pass through appropriate approval steps before being implemented. Any change to the protocol constitutes an amendment.

Where the amendment affects the ongoing suitability of the study at a participating site, Research Governance approval will also be sought. The Research Governance Office will determine the ongoing suitability based on the amendment submitted.

The Coordinating Principal Investigator will submit the amendment to the appointed HREC for their approval; written approval will be obtained. Completed and signed Protocol amendments will be circulated to all appointed site Investigators.

### **Version Control**

Version control ensures that amendments to documents are tracked and verifiable and that the correct version of a document is in use according to the relevant ethical, regulatory or local approval.

All documents will be given a version number and date e.g., Version 1.0 15-Feb-15

Each amendment to a document will require a version number and date to be updated.

If this is a **significant change** e.g., change in the content of the document, then the version number will be increased by 1.0.

If it is a **minor change** e.g., contact details, then the number after the decimal point will be increased by 0.1.

### **Protocol Compliance**

Should there be questions or consideration of deviation from the Protocol, clarification will be sought from the Coordinating Principal Investigator. Any participant treated in a manner that deviates from the Protocol, or who is admitted into the study but is not qualified according to the Protocol, will be ineligible for analysis.

If an emergency occurs that requires a departure from the Protocol, the nature and reasons for the Protocol violation/deviation will be recorded in the CRF and the Coordinating Principal Investigator will notify the Reviewing HREC and /or Governance Office as soon as possible.

Whilst the Coordinating Principal Investigator has overall responsibility for the conduct of the study, the appointed site Investigators will have the responsibility to ensure all study personnel at their sites comply with GCP, National Statement on Ethical Conduct (2007), Australian Code for the Responsible Conduct of Research and local policies and procedures.

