#### **3.1 Interventions**

**CIRCuiTs (Computerised Interactive Remediation of Cognition – Training for Schizophrenia).** This is a modular computer package including tasks of a wide range of cognitive functions (particularly executive function and memory). CIRCuiTs are run for 1 hour twice a week for 12 weeks and is delivered through a computer. CIRCuiTS consist of 40 stages. Twenty sessions are considered an adequate treatment exposure and 20 minutes a “session”.

In this study 20 participants with schizophrenia (intervention group) will have one face to face meeting with the therapist to orientate to the program. These participants will then complete the program (40 sessions or 12 weeks of at least 20-minute session twice a week) either online or in-

person, and independently or in a group. The therapist will have telephone (duration <1 hour) contact once a week to support online participation. Only the intervention group will complete these sessions.

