### **3.2 Study Population**

#### **3.2.1 Intervention and treatment as usual patient groups**

Participants (n=40) with a diagnosis of a schizophrenia spectrum disorder, based on current medical records will be recruited from the teams of the Metro South Addiction and Mental Health service (MSAMHS). Participants (n=20) that are not interested in completing CR will form the patient TAU control group and will complete the pre and post measures only. Thus, group intervention allocation selection will be based on individuals' preference to participate in CR. If a participant initially signs up to the intervention group but due to change in circumstances is unable to complete CR, they will be offered the opportunity to become part of the TAU group. Individuals that initially choose to complete CR therapy but then fail to complete more than 5 sessions will be re-allocated to the control (treatment as usual) group.

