### **8.1 Participant Withdrawal by the Investigator**

Worsening of mental state such that the patient is admitted to hospital or their ability to provide ongoing informed consent is compromised.

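### The protocol bars from analysis anyone whose treatment deviated, with no threshold; the exclusion is post-baseline, falls mainly on partly exposed CR participants and conflicts with the protocol's other exposure rules

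*Protocol*

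**What the plan says.** Under Protocol Compliance, any participant treated in a way that "deviates from the Protocol, or who is admitted into the study but is not qualified according to the Protocol, will be ineligible for analysis". The sentence has two limbs.

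- **Treatment:** "Any participant treated in a manner that deviates from the Protocol" is made ineligible for analysis.
- **Eligibility:** so is anyone "admitted into the study but is not qualified according to the Protocol, will be ineligible for analysis".

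Neither limb separates major from minor departures. Section 9 defines no analysis population that would override the sentence; Section 9.2 simply applies 3 x 2 mixed ANOVAs to each outcome.

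Other sections bear on who can deviate, and on what happens to people with little exposure:

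- Section 3.1 sets the CR course at "40 sessions or 12 weeks of at least 20-minute session twice a week" and adds: "Only the intervention group will complete these sessions". It also states: "Twenty sessions are considered an adequate treatment exposure".
- Section 3.2.1 says that TAU patients "will complete the pre and post measures only". CR participants who do not get beyond 5 sessions are re-allocated to TAU, and those who can no longer complete CR because their circumstances change are offered a place in TAU. Allocation is by participant preference.
- Section 8 counts 20 sessions plus the end assessment as completion for the intervention group.

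**The concern.** The treatment limb selects on something that happens after baseline. TAU has assessments but no study treatment, and healthy controls do only the fMRI task, so a rule about how a participant was treated bears mainly on CR. Adherence to a cognitive training programme may well be related to how much a participant changes. If it is, the analysed CR group is a selected subset compared with an unselected TAU group, and part of any CR-TAU difference is produced by the rule.

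Two further costs follow. With 20 per group, each deleted CR participant is 5% of the arm. Deletion from analysis also removes that person's baseline scan and scores, although Hypotheses 1A and 2A concern patients' deficits, for which later adherence to CR is irrelevant.

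The rule also cannot be applied consistently. A deviation is not defined, questions about deviation go to the Coordinating Principal Investigator, and nothing requires deviations to be classified before outcomes are seen.

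**Working it through.** **Step 1. What the text does at each level of CR exposure.** Twelve weeks at two sessions a week is 12 x 2 = 24 sessions; the alternative target is 40.

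| CR sessions done | Sections 3.1, 3.2.1 and 8 | Protocol Compliance |
|---|---|---|
| 5 or fewer | Moved to TAU and kept | Not a deviation if Section 3.2.1 is followed |
| 6-19 | Not a completer; TAU place offered if circumstances change; otherwise nothing stated | Can be excluded |
| 20-23 | Adequate exposure; completer once the end assessment is done | Short of both 24 and 40, so arguably excluded |
| 24 over 12 weeks, or 40 | As prescribed | Kept |

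Read together, the sections may keep someone with 5 sessions (as TAU) and delete someone with 15. Someone with 21 can be both a completer and a deviator.

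**Step 2. Possible bias.** The protocol gives no power calculation, adherence rate or outcome SD, so there is no figure to reproduce. Let q be the share of CR excluded (the least adherent) and ρ the correlation between adherence and change in outcome. Both are assumptions. With no true CR effect and a normal model, the CR mean is shifted by

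bias (in SD) = ρ × φ(z_q) / (1 − q),

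where z_q is the q-quantile of the standard normal distribution and φ its density.

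| q | CR kept of 20 | φ(z_q)/(1 − q) | ρ = 0.2 | ρ = 0.3 | ρ = 0.5 |
|---|---|---|---|---|---|
| 10% | 18 | 0.195 | 0.039 | 0.058 | 0.097 |
| 20% | 16 | 0.350 | 0.070 | 0.105 | 0.175 |
| 30% | 14 | 0.497 | 0.099 | 0.149 | 0.248 |
| 40% | 12 | 0.644 | 0.129 | 0.193 | 0.322 |

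The range is 0.04 to 0.32 SD. At ρ = 0 it is zero.

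**Step 3. False-positive rate.** Simulation with 40,000 runs, 20 per group, no true effect and a two-sided t-test at 0.05 on one outcome:

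| q | ρ | Mean CR-TAU difference (SD) | False-positive rate |
|---|---|---|---|
| 20% | 0.3 | 0.098 | 0.060 |
| 20% | 0.5 | 0.168 | 0.081 |
| 30% | 0.3 | 0.143 | 0.071 |
| 30% | 0.5 | 0.238 | 0.107 |
| 40% | 0.3 | 0.188 | 0.077 |
| 40% | 0.5 | 0.306 | 0.133 |

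Keeping all 20 CR participants gives 0.048 to 0.053. The simulated shifts are slightly below the formula because the groups are small. The exercise isolates the exclusion rule; it includes neither confounding from preference-based allocation nor re-allocation to TAU.

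**Step 4. Precision.** In SD units the standard error of the CR-TAU difference is √(1/n_CR + 1/20).

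- 20 kept: √(1/20 + 1/20) = 0.316.
- 18 kept: √(1/18 + 1/20) = 0.325; variance ratio 0.1000/0.1056 = 0.947, a 5% loss of information.
- 15 kept: √(1/15 + 1/20) = 0.342; ratio 0.1000/0.1167 = 0.857, a 14% loss.
- 12 kept: √(1/12 + 1/20) = 0.365; ratio 0.1000/0.1333 = 0.750, a 25% loss.

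**The case against.** The strongest defence is that the study asks about completers. Aim 1 concerns a course of at least 20 sessions, Hypothesis 1B concerns participants who complete CR, and Section 9.1 calls this a pilot of mechanism rather than of effectiveness. Allocation is by preference, so there is no randomisation for an all-enrolled analysis to protect. It stands that an exposure-restricted analysis has a place here. But such an analysis needs a fixed threshold. Section 8 supplies one, and the compliance sentence can exclude beyond it and removes baseline data as well. Existing confounding is no reason to add an avoidable selection.

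A reader might infer more than the documents support:

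- **That one missed week means deletion.** One missed week leaves 22 of 24 sessions, above the 20 that Sections 3.1 and 8 accept. The sentence sits in administrative text about seeking clarification and emergency departures, and does not mention attendance. The text leaves the matter open.
- **That it overrides the move to TAU.** Following Section 3.2.1 is not a deviation. The unresolved cases are those above 5 sessions who fall short of the course and do not join TAU.
- **That Section 8.1 makes the loss one-sided.** Its criterion ("Worsening of mental state such that the patient is admitted to hospital") is not limited to CR, and the section does not say that data already collected are discarded.
- **That an inflated CR effect is established.** Size and direction depend on adherence and its link to outcome, which the documents do not give.
- **That the whole sentence is a post-baseline exclusion.** The eligibility limb concerns status at entry and is defensible.

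**Conclusion.** The point holds for the treatment limb. It is an explicit rule with no threshold and no alternative analysis set, so a statistical analysis plan that kept these participants would contradict the protocol. That it falls mainly on CR is an inference, but a sound one, because no other group has a study treatment. The conflict among Sections 3.1, 3.2.1, 8 and Protocol Compliance is textual and needs no assumption.

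The size is illustrative. Under the assumed ranges the spurious CR-TAU difference is 0.04 to 0.32 SD, and the false-positive rate in the simulated cases is 0.060 to 0.133 against about 0.05. Bias in favour of CR is the likely direction if poorer adherers improve less; if adherence is unrelated to change, the harm is lost precision and discarded baseline data. Any such bias adds to the confounding from preference-based allocation, which correcting the rule will not remove.

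**What to change.** 1. Under Protocol Compliance, delete treatment deviation as a ground for exclusion. Keep the exclusion of participants who did not meet eligibility at baseline. Possible wording: *All eligible participants are analysed in the group they first entered, using all available data. Deviations are recorded and listed. Participants found not to have met the eligibility criteria at baseline are excluded.*
2. Use an analysis that accepts participants with one assessment, for example a mixed model for repeated measures instead of the two-time-point ANOVA in Section 9.2, which needs both. Keep all eligible participants' baseline data for Hypotheses 1A and 2A.
3. Add a predefined completer (per-protocol) set for Hypothesis 1B, using the protocol's own 20-session definition, with deviations classified before outcome data are seen. Report it as an additional analysis.
4. Reconcile Sections 3.1, 3.2.1, 8 and Protocol Compliance, and state that re-allocation under Section 3.2.1 does not change the analysis group. The meaning of a session needs reconciling too: Section 3.1 counts 20 minutes as a session, while Section 8 equates 20 sessions with 20 hours.

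The withdrawal rule in Section 8.1 is not questioned.

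Cost: a protocol amendment and slightly more analysis work. The estimated CR effect may be somewhat smaller.

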**Archives: Retention of Study Records**

All documentation will be kept by the Investigators for at least 7 years, or the maximum time frame as determined by local regulations, whichever is the longest.

